#### Screening Tests

After obtaining informed consent (approach detailed in section A6), authorized members of the study team will conduct screening assessments.

1. Confusion Assessment Method (CAM): Trained assessors will administer the CAM to enrolled participants to identify those with delirium. Patients identified as CAM positive will be excluded.
2. Montreal Cognitive Assessment (MoCA): Trained assessors will administer the MoCA to enrolled participants to identify those with undiagnosed, early stage cognitive decline. Patients with a MoCA score below 23 points will be excluded. The test ranges from 0 [worst] to 30 [best], with 26 and above typically considered “normal” range.

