### Questionnaires/Assessments

- Richards-Campbell Sleep Questionnaire (RCSQ): The RCSQ is a validated instrument for assessing sleep and evaluates subjective perceptions of depth of sleep, time to sleep onset, number of awakenings, time spent awake, and overall sleep quality. Each of these five items is assessed using visual analogue scales (each from 0 [worst value] to 100 [best value]). The participant will be asked to use a slider to mark the answer on the scale in the electronic version of the questionnaire or mark an "X" on the paper version.
- Montreal Cognitive Assessment (MoCA): The MoCA Test is a validated tool to quickly assess a patient's cognitive health and detect cognitive impairment. The assessment consists of a one-page test and evaluates several cognitive domains: Short-term memory, visuospatial abilities (clock-drawing), executive functions (trail-marking), attention, language, abstraction, and orientation. The score point values range from 0 [worst] to 30 [best], with 26 and above typically considered "normal" range.
- Confusion Assessment Method (CAM): The CAM is a standardized screening tool used for identification of delirium symptoms. It consist of two parts: Part one screens for overall cognitive impairment, while part two focuses on the 4 features found to have the greatest ability to distinguish delirium from other types of cognitive impairment. Those features of delirium include acute onset and fluctuating course, inattention, disorganized thinking, and altered level of consciousness. The CAM-ICU (a modified version of the CAM for use in ICU patients) includes both brief cognitive testing and the CAM algorithm to screen for delirium.
- Delirium Symptom Interview (DSI): The Delirium Symptom Interview is a standard cognitive assessment assessing areas such as disorientation and perceptual disturbance. The instrument can be administered on a daily basis to track symptoms over time. Each item is scored as present or absent and subscores are created for each assessed area.

**Figure 2.** Illustration of study procedures

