## Study endpoints

1. Primary outcome: duration of nighttime wakefulness after persistent sleep onset (WASO) during the first night in the cardiac ICU.
2. Secondary outcome: total sleep time (TST) during the night of the sleep trial in the cardiac ICU.
3. Exploratory outcomes:
  - a) incidence of postoperative in-hospital delirium
  - b) number of delirium free days,
  - c) time to sleep onset (TSO) during the night of the sleep trial,
  - d) effect modification by distinct perioperative factors leading to insomnia in the ICU, such as procedural severity, patients' comorbidities, circadian disruption, and pharmacological treatment with centrally acting drugs.

The following baseline variables will be collected: Clinical and demographic variables will be collected including age, gender, body mass index, type and severity of chronic lung disease, ASA class, history of obstructive sleep apnea, smoking history, hypertension, coronary artery disease, heart failure, cerebrovascular accident or neurologic dysfunction, chronic kidney disease, diabetes mellitus, Charlson comorbidity index and Procedural Severity Score. Additionally, to track other important intraoperative and postoperative factors related to overall patient outcome, we will record administrative, demographic, clinical and billing data including: vital signs, medications administered, length of operation, type of operation, duration of mechanical ventilation, duration of bypass time, total blood loss, blood transfusion, postoperative complications, ICU length of stay prior to drug administration.

We will also record nursing-patient interactions (e.g. intravenous line placement, IV flushing, blood sampling, turning/positioning of patients, wound care, breathing treatments, medication administrations, vital sign checks, neurological checks, point-of-care glucose measurements, and patient-initiated contacts).

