#### Primary and secondary analyses

The primary and secondary analyses will be by intention-to-treat and will compare WASO and TST between patients receiving suvorexant or placebo. Baseline characteristics of the two groups will be presented descriptively. Normally distributed continuous variables will be expressed as means and standard deviations, non-normally distributed variables as medians and interquartile ranges, and categorical variables as frequencies and percentages. We will calculate the standardized differences of baseline characteristics between the two groups. To determine whether times of WASO and TST differ between treatment groups, we will analyze our data using a Student's t test, or Mann-Whitney-U test, as appropriate.

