#### *Delirium*

To determine whether incidence of postoperative delirium and delirium free days differ between treatment groups, we will analyze data analogously to the primary and secondary analyses.

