### Primary Exclusion criteria:

1. Preoperative left ventricular ejection fraction of less than 30%
2. Renal failure (creatinine >2 mg/dl or dialysis dependence)
3. Liver failure (CHILD-Pugh score > 6)
4. Coma (RASS<-1)
5. Signs and symptoms of delirium and agitation at time of enrollment (CAM-ICU positive)
6. Montreal Cognitive Assessment (MoCA) below 23 at time of consent
7. Psychiatric or neurologic diseases (including chronic benzodiazepine use, bipolar disorder, psychotic disorder, posttraumatic stress disorder, requirement of prophylactic psychiatric medication, evidence of acute depression on screening visit, preexisting cognitive impairment, Alzheimer disease, Parkinson's disease, medications for cognitive decline, history of recent seizures (within 1 year prior visit), alcoholism or documented history of alcohol abuse, and narcolepsy)
8. Severe sleep apnea requiring home CPAP treatment
9. Morbid obesity (BMI >40)
10. Known or suspected pregnancy (there are no adequate and well-controlled studies of suvorexant in pregnant women. Based on animal data, Suvorexant may cause fetal harm).
11. Patients with known hypersensitivity to study medications
12. English language limitations (Sleep assessment and delirium assessment tools are only validated in English)
13. Patients enrolled in other interventional studies which could confound the primary endpoint.

Participants who do not speak English will be excluded because of their inability to complete the cognitive assessments, which have been extensively validated in English. Adult patients unqualified or incapable of giving legal consent will be excluded. Secondary exclusion criteria after enrollment will include massive intraoperative hemorrhage, postoperative respiratory failure, loss of enteral access and signs and symptoms of delirium and agitation at time of study drug initiation (CAM ICU positive) . An overview of eligibility criteria is provided in **Figure 3**.

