### Consent

Once a patient is found eligible and after notifying the clinical care team, authorized study team members will obtain written informed consent from all participants prior to surgery and initiation of study procedures. Consent will be obtained by trained study staff with doors closed/curtains drawn to assure patient privacy. Trained study team members will introduce the study to the prospective participant. The study physician will be present to answer questions, describe the study, and sign the consent form with participants. All study procedures including associated risks and benefits will be explained in detail. All questions asked by subjects will be answered. Subjects will be informed that participation is voluntary and that they can withdraw consent at any time. Study staff will conduct a screen for comprehension and capacity during the consent conversation. Methods include asking questions such as: "we're asking you to make an important choice. I need to check if we've done a good job explaining everything. May I ask you a few questions? What condition have you been treated for? What are the researchers trying to find out? What would you do as part of the study?" If a patient is not able to answer the screening questions comfortably or if any doubt about a patient's competency to sign the consent form arises, the patient will not be enrolled in the study. The original signed consent form will be stored in the study binder. We will provide a copy of the consent form to the patient. Another copy will be stored in the patient's medical record. The study team undergoes standardized, rigorous training regarding the informed consent process for research.

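### The preoperative MoCA score serves only as an entry cut-off, and the exploratory delirium outcomes are compared without covariates, which gives up a modest amount of precision

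*Combined protocol and SAP*

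**What the plan says.** **Measurement.** Under Screening Tests (B3.A): "Trained assessors will administer the MoCA to enrolled participants to identify those with undiagnosed, early stage cognitive decline". The section Consent (B6) fixes the timing: "authorized study team members will obtain written informed consent from all participants prior to surgery and initiation of study procedures". Randomization follows extubation (Randomization and blinding), so MoCA is a genuine pre-randomization covariate.

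**Stated use.** There is one. Screening Tests: "Patients with a MoCA score below 23 points will be excluded". The exclusion list repeats it: "Montreal Cognitive Assessment (MoCA) below 23 at time of consent". Randomized patients can therefore score from 23 to 30, which includes 23–25, below the 26 that the protocol describes as the usual lower limit of normal.

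**Where MoCA is not named.** The baseline list under Study endpoints runs from age to "chronic kidney disease, diabetes mellitus, Charlson comorbidity index and Procedural Severity Score" without it. It is not among the effect modifiers under Variability in response to suvorexant treatment. The only stratification factor is perioperative sedation, split at 420 minutes.

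**Delirium analysis.** For both incidence and delirium-free days, the section Delirium under Exploratory analyses says "we will analyze data analogously to the primary and secondary analyses". Those analyses read "we will analyze our data using a Student's t test, or Mann-Whitney-U test, as appropriate". No covariate is named. The only regression models in the plan have total sleep time as their outcome.

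**The concern.** Baseline cognition is a natural candidate predictor of postoperative delirium. The protocol itself treats it as relevant by screening for early decline and excluding known impairment. With about 50 patients per arm and no stratification on cognition, the arms can differ on MoCA by chance. An unadjusted test does not correct for that, and it leaves in the error term any variation that MoCA explains.

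The delirium estimates have a declared purpose. The section Assessment of delirium (B2) says the study will inform effect sizes for later trials, and Sample Size Justification quotes a power for delirium-free days. Precision therefore matters somewhat, even for exploratory outcomes.

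A second point concerns the same sentence. Analysing incidence in the same way as WASO and TST means a t or Mann-Whitney test on a yes/no outcome, so the method for incidence needs to be restated in any case.

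**Working it through.** **Inputs from the documents.** 50 per group; 3-day difference and SD 5 for delirium-free days; stated power 84.4%; two-sided alpha 0.05 (Sample Size Justification). Expected delirium incidence 28.3% (Preliminary data, Delirium in the ICU).

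**Inputs assumed.** The documents give no MoCA distribution and no association with delirium. Both are therefore shown as ranges.

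**1. The plan's own power figure.** The standard error of the difference is 5 × √(2/50) = 1.0 day, so the noncentrality is 3/1.0 = 3.0 with 98 degrees of freedom. The noncentral t distribution gives 84.39%, which matches 84.4%. The stated power is that of an unadjusted t test.

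**2. Delirium-free days with adjustment.** If ρ is the correlation of MoCA with delirium-free days, the residual SD is 5 × √(1 − ρ²) and the equivalent unadjusted sample is 100/(1 − ρ²).

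| ρ (assumed) | Residual SD | Power | 95% CI half-width, days | Equivalent N |
|---|---|---|---|---|
| 0 | 5.000 | 84.4% | 1.984 | 100 |
| 0.1 | 4.975 | 84.7% | 1.974 | 101 |
| 0.2 | 4.899 | 85.8% | 1.944 | 104 |
| 0.3 | 4.770 | 87.6% | 1.893 | 110 |

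Correlations of 0.4 and 0.5 would give 90.0% and 92.9%. They are less plausible because the cut-off at 23 narrows the score range.

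**3. Chance imbalance, delirium-free days.** The standardized MoCA difference between arms has standard error √(2/50) = 0.20, so it exceeds 0.2 in absolute value about 32% of the time. An imbalance of 0.2 SD shifts the unadjusted difference by ρ × 0.2 × 5, which is 0.1 to 0.3 days for ρ of 0.1 to 0.3. The standard error is 1.0 day and the assumed effect 3 days.

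**4. Incidence.** The standard error of the risk difference is √(2 × 0.283 × 0.717/50) = 0.090. Let q be the share scoring 23–25, p₁ their delirium risk, and p₀ = (0.283 − q·p₁)/(1 − q) the risk in the rest. Then:
- R² = q(1 − q)(p₁ − p₀)²/(0.283 × 0.717)
- extra patients per 100 = 100 × R²/(1 − R²)
- shift for a one-SD imbalance = (p₁ − p₀) × √(2q(1 − q)/50)

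| q | p₁ | p₀ | R² | Extra patients per 100 | Shift, percentage points |
|---|---|---|---|---|---|
| 0.30 | 0.32 | 0.267 | 0.003 | 0.3 | 0.5 |
| 0.30 | 0.40 | 0.233 | 0.029 | 3.0 | 1.5 |
| 0.40 | 0.45 | 0.172 | 0.092 | 10.1 | 2.7 |

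The largest shift is 2.7/9.0 = 0.30 standard errors.

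**5. Power for incidence by simulation.** There were 2,000 runs per setting, 28.3% against an assumed 10%, 50 per arm, with likelihood-ratio tests. Power without and with adjustment was 67.9% and 68.9% at an odds ratio of 1.25 per SD of the score, 67.3% and 68.0% at 1.5, and 67.3% and 70.3% at 2.0. With no association the pair was 67.8% and 68.1%, so differences of a fraction of a point mean little. The gain is about 1 to 3 points.

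**The case against.** The strongest reply is that nothing here is wrong. An unadjusted comparison of randomized arms is unbiased, and its standard error already allows for chance imbalance in MoCA. The delirium outcomes are exploratory, so leaving out covariates is a permissible choice. The entry criteria also narrow the problem: they remove scores below 23, known cognitive impairment and drugs for cognitive decline. All of this stands, and it is why the point is small.

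Three stronger readings are tempting, and the documents do not support them.

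- **A reader might infer that MoCA is discarded and its balance will go unchecked.** The baseline list under Study endpoints is introduced as open-ended, and the standardized differences promised under Primary and secondary analyses are not limited to that list. MoCA may well be tabulated. What can be said is that the plan does not name it, and that a table would not adjust the comparison.
- **A reader might infer that the delirium result would be biased.** It would not. The loss is efficiency, plus protection conditional on the imbalance that happens to occur.
- **A reader might take a gain of 3 to 10 patients per 100 as established.** That range presupposes that patients scoring 23–25 have roughly twice the risk of the others or more. A weak association takes the gain to near zero.

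The figure of 28.3% may also be too high here. It comes from a similar cohort, and this trial excludes patients who are CAM-ICU positive when study drug is due to start.

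**Conclusion.** The point holds as a minor, low-cost improvement. MoCA is available before randomization in every enrolled patient, its only stated use is the cut-off, and no planned delirium analysis includes a covariate. The method that the plan borrows for incidence does not suit a binary outcome.

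For incidence, adjusting for a split at 23–25 is worth between about 0.3 and 10 patients per 100, with R² from about 0.003 to 0.09. For delirium-free days, power moves from 84.4% to about 84.7–87.6% at correlations of 0.1–0.3. Both ranges rest on an association that the documents do not report. The primary WASO comparison and the secondary TST comparison are outside this point.

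**What to change.** 1. Name the MoCA score among the baseline variables under Study endpoints, so that it clearly enters the balance table.
2. In the section Delirium under Exploratory analyses, replace the reference to the primary and secondary methods with two stated models, fixed before unblinding:
   - incidence: logistic regression on treatment, MoCA (continuous), age and the sedation-duration stratum (420 minutes or more against less), reporting the standardized risk difference with its 95% confidence interval;
   - delirium-free days: a regression with the same covariates, reporting the adjusted difference with its 95% confidence interval.
3. Keep an unadjusted comparison of each outcome as supportive. For incidence, use a test suited to a binary outcome.
4. Do not lengthen the covariate list. At 28.3% of 100 patients there would be about 28 events for four coefficients, or about 7 per coefficient, and possibly fewer.

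The cost is a few lines of SAP text and two regression models. MoCA, age and sedation duration are already collected, so no visit, measurement or patient is added. Timing matters: the same adjustment introduced after unblinding could look selective.

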#### Randomization and blinding

After postoperative extubation, eligible patients will be randomly allocated in a 1:1 ratio to receive either suvorexant 20 mg or placebo. If extubation is planned outside of research pharmacy hours, randomization and drug preparation will take place in coordination with research and hospital pharmacy in accordance with their policy. Randomization will be performed by computer-generated variable block size random allocation stratified by duration of perioperative anesthesia and sedation, using a cut-off value of 420 minutes of perioperative sedation (i.e. duration of anesthesia and postoperative sedation of equal to or over 420 minutes). The allocation sequence will be provided to the research pharmacy. To achieve blinding, the study drug and placebo will be delivered in the form of non-identifiable pills, containing either the active ingredient suvorexant, or lactose. Individual patients' drug bottles will be labeled with randomization numbers. Randomization number-specific codebreakers, prepared by the research pharmacy, will contain information about a patient's treatment allocation in a sealed envelope and will be kept in the patient's study record. If unblinding procedures are necessary for clinical reasons, the clinical team will be able to contact a member of the research team with access to the codebreaker at any time by pager or phone. The codebreaker envelope is only to be opened with PI approval as instructed on the envelope. The PI will immediately inform the research pharmacy and study team of any unblinding procedures. Delivery of research medication to the patient care area will take place per pharmacy guidelines. Disposal of any unused study medication will be done per pharmacy guidelines.

#### Study interventions

Suvorexant 20 mg or placebo will be administered p.o. once a day at 9:00 pm for a maximum of 7 days starting the night after extubation in the ICU. A one-hour window (9:00 pm-10:00 pm) to administer the drug will ensure protocol adherence in case of delays in drug administration. Prior to every study drug administration, the Richmond Agitation-Sedation Scale will be assessed. In case of RASS < -1, the study drug will not be administered on that same day. The study drug will be discontinued:

1. After 7 consecutive doses following extubation; or

2. At hospital discharge (if less than 7 days after extubation); or
3. At ICU discharge, if patient showed signs of airway obstruction during sleep; or
4. At ICU discharge or after a maximum of 3 consecutive doses, whichever occurs sooner, if strong inhibitors of CYP3A (e.g. digoxin, diltiazem, verapamil) are co-administered; or
5. In the event of early termination: subject withdraw of consent, investigator withdrawal for toxicity or other reasons.

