## B3. DESCRIPTION OF RESEARCH PROTOCOL

### A. Study Design – Overview, Methods, Procedures

#### Study design & overview

- This is a single-center, randomized, double-blind, placebo-controlled trial expected to enroll 120 subjects. Participants will be enrolled preoperatively and randomized in a 1:1 ratio to receive suvorexant or placebo. Prior to randomization, informed consent will be obtained from all participants. The patient is first asked to report information about their sleep using the Richards-Campbell Sleep Questionnaire (RCSQ). Patients will be asked to complete a sleep questionnaire for at least one night before surgery or, if possible, daily, starting 3 days before surgery. The questionnaire will be performed online in RedCap; patients will be emailed a link to the survey. If patients do not have access to an internet-enabled device, they will be handed the RCSQ on paper and asked to complete it before surgery. The intervention (study drug) will be applied for 7 nights starting the night after postoperative extubation in the ICU. Primary and secondary outcomes will be assessed once during the night of the sleep trial in the ICU. The sleep trial will take place during the first night after extubation if the patient has been extubated before 7pm. If patient is extubated after 7:00 pm study medication will be administered the night after extubation only if still in ICU.

Exploratory outcomes will be assessed from day of extubation until hospital discharge. An outline of the study procedures is provided in **Figure 2**.

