The primary outcome will be Wakefulness After persistent Sleep Onset (WASO). WASO will be defined as the duration of wakefulness after the onset of persistent sleep in the observation period between 10 PM (Lights-Off) to 6 AM (Lights-On) in minutes [24]. Onset of persistent sleep will be defined on the EEG as the first epoch of 10 consecutive minutes of sleep (REM or non-REM Stages 1, 2, 3 or 4) after Lights-Off. Wakefulness will be defined as any epoch of Stage 0.

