## B6. RECRUITMENT AND CONSENT PROCEDURES

### Recruitment

Eligible participants will be identified on the medical or surgical floors, at pre-admission testing clinic appointments, or in the cardiac catheterization lab with all inclusion and exclusion criteria assessed at this time. Members of the study team will screen operating room schedules, patient medical records and appointment schedules for the presence of inclusion or exclusion criteria to determine eligibility for enrollment. A secure screening and enrollment log will be kept. If a patient is deemed a potential candidate, they will be approached for informed consent by authorized team members.

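### The single EEG night is set by extubation time while a RASS hold can withhold that night's dose, so WASO can be measured on a night without study drug

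*Combined protocol and SAP*

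**What the plan says.** **Which night is measured.** Under Study design & overview: "Primary and secondary outcomes will be assessed once during the night of the sleep trial in the ICU". The same section fixes that night for most patients: "The sleep trial will take place during the first night after extubation if the patient has been extubated before 7pm". For later extubation it says when drug is given, without naming the EEG night: "If patient is extubated after 7:00 pm study medication will be administered the night after extubation only if still in ICU". The Primary objective and Study endpoints sections instead place the primary outcome on the first night in the cardiac ICU.

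**When drug is withheld.** Under Study interventions, RASS is assessed before every administration: "In case of RASS < -1, the study drug will not be administered on that same day". This is a one-day hold. It is not among the five listed reasons for discontinuing study drug.

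**How the outcome is scored and analysed.** WASO is counted "in the observation period between 10 PM (Lights-Off) to 6 AM (Lights-On) in minutes", with no condition that a dose was given. "The primary and secondary analyses will be by intention-to-treat".

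**Eligibility.** RASS below -1 is a primary exclusion (item 4), and the Recruitment section has patients identified before surgery "with all inclusion and exclusion criteria assessed at this time". Randomization of eligible patients follows extubation. The secondary exclusions after enrollment include "signs and symptoms of delirium and agitation at time of study drug initiation (CAM ICU positive", but do not name RASS.

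**The concern.** Two rules run on different clocks. The measured night follows from the time of extubation; whether drug is given that evening follows from RASS at about 9 pm. Take a patient extubated at 4 pm, randomized, and found at RASS -2 at 9 pm. No study drug is given, but by the stated schedule that night is still the sleep trial. Drug may start the next evening, when no further WASO measurement is planned.

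In the suvorexant arm such a patient adds an untreated night to the primary and secondary comparisons, and does so on a night marked by residual sedation. The trial then understates what the drug does on a treated night and loses power, although the patient may go on to be dosed. The increase from 100 to 120 enrolled patients covers those who do not complete. It does not cover completed recordings made without drug.

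**Working it through.** **Inputs from Sample Size Justification:** difference 30 minutes, SD 45 minutes, 50 per group, two-sample t-test, two-sided alpha 0.05, stated power above 90%.

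**Assumed input:** p, the share of first doses held on the sleep-trial night. The documents give no rate, so 3%, 5% and 10% are shown. Held patients in the suvorexant arm are assumed to show no drug effect that night, and 30 minutes is taken as the difference if everyone is dosed.

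**Step 1: reproduce the plan's figure.** Noncentrality = 30 / (45 × √(2/50)) = 30 / 9 = 3.33 on 98 degrees of freedom. Exact t power is 91.0% (normal approximation 91.5%), in agreement with the plan. The margin above 90% is about one point.

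**Step 2: keep undosed nights in the comparison.** The suvorexant arm becomes a mixture of dosed and undosed nights.

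- Expected difference = 30 × (1 − p)
- Suvorexant-arm variance = 45² + p(1 − p) × 30²
- Pooled SD = square root of the mean of that variance and 45²

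| p | Difference (min) | Suvorexant-arm variance | Pooled SD | Power, 50 per group |
|---|---|---|---|---|
| 0 | 30.0 | 2025.00 | 45.00 | 91.0% |
| 3% | 29.1 | 2025 + 26.19 = 2051.19 | 45.15 | 89.1% |
| 5% | 28.5 | 2025 + 42.75 = 2067.75 | 45.24 | 87.7% |
| 10% | 27.0 | 2025 + 81.00 = 2106.00 | 45.45 | 83.7% |

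Holding the SD at 45 changes little: 89.3%, 88.0% and 84.4%. On that basis, power passes below 90% at a hold rate of about 1.8%.

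**Step 3: move the EEG to the first dosed night, worst case.** Suppose every held patient leaves the ICU before a first dose and has no outcome. Both arms shrink by p and the difference stays at 30 minutes. At p = 10%, n = 50 × 0.9 = 45 per group. Noncentrality = 30 / (45 × √(2/45)) = 3.16, and power is 87.9%, against 83.7% in step 2. At p = 5%, rounding 47.5 down to 47 per group gives 89.2%, against 87.7%. Any held patient who is later dosed and recorded in the ICU improves on these figures.

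**Step 4: direction.** A hold on the first night is decided before that patient has had any study drug, by staff who do not know the allocation. Its frequency cannot depend on arm except by chance. The result in step 2 is therefore attenuation toward no difference.

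**The case against.** The strongest reply is that the plan never says an undosed night is to be recorded. The 7 pm cut-off sits before the 9 pm dose, and the sentence on late extubation is about when drug is given. Both suggest that the sleep trial was meant to fall on a dosed night. The study-procedure and eligibility figures are not visible in the copy reviewed and might say more. This stands as to intent, but the rules as worded, followed literally, still produce an undosed measured night.

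A second reply is that intention-to-treat legitimately keeps undosed patients, and that moving the night changes the question and mixes postoperative nights. That is fair. However, the choice of measured night is a matter of endpoint definition. A definition triggered by the first blinded dose, active or placebo, keeps the arms comparable.

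Third, the number affected may be small. Altered consciousness is one of the four CAM features, so the CAM-ICU exclusion at drug initiation may remove some over-sedated patients, and a check of eligibility at randomization is possible. Neither provision names RASS below -1, so the protection is partial.

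A reader might also infer that the RASS exclusion and the RASS hold contradict each other, or that the exclusion can never apply. The documents do not support this. The two rules operate at different times, and item 4 carries no time point of its own; only the general statement in Recruitment places it before surgery. Nor do they support an inference that the comparison is biased in favour of an arm.

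**Conclusion.** The point holds as a gap between the measurement rule and the dosing rule: the plan's own wording allows an undosed night to enter the primary intention-to-treat comparison. The consequence is dilution. Its size depends on a hold rate that the documents do not give and on the assumption of no effect in held patients: about 2 points of power at 3% held, about 3 at 5%, and about 7 at 10%. The low end is the more cautious expectation, given the CAM-ICU check. A reader might conclude that the trial is seriously underpowered; nothing in the documents establishes that. The change is worth making because it is inexpensive, the planned margin above 90% is only about one point, and the alternative keeps more power even when every held patient is lost.

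**What to change.** In Study design & overview and in the Primary outcome assessment section, define the night of the sleep trial as the first night in the ICU on which blinded study drug (active or placebo) is actually administered, so that the single EEG recording moves with a held first dose. Use the same definition in the Primary objective and Study endpoints sections, which now refer to the first night in the cardiac ICU. It should also name the EEG night for patients extubated after 7 pm.

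State in the analysis section how randomized patients with no sleep-trial night are handled, and report by arm the number with a held first dose and the number with no such night.

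Separately, reconcile the RASS entry among the primary exclusions, assessed at recruitment, with the RASS check before each dose. No clinical rule is proposed here.

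The cost is protocol wording; there is still one EEG night per patient. The downside is that a held patient who leaves the ICU before a first dose has no primary outcome, so the comparison covers patients who received a first blinded dose in the ICU. That loss is settled before any study drug and is independent of arm.
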